4.1 Data and Safety Monitoring Committee

Data and Safety Monitoring will be conducted by the Principal Investigators and the Study Physician. They will review all possible Adverse Events (AEs) and Serious Adverse Events (SAEs). They will ensure that this information is captured in a comprehensive manner and reported according to Good Clinical Practice (GCP). The Principal Investigators, Study Physician, and the research staff will oversee and complete the monitoring process. Monitoring will be performed on an ongoing basis in accordance with the University of Pennsylvania Sponsor-Investigator Standard Operating Procedure PM 504.

The Principal Investigators are responsible for:

1. Obtaining IRB review and approval of a clinical investigation before the investigation is initiated and ensuring continuing review of the study by the IRB in accordance with 21 CFR Part 56;
2. Obtaining informed consent in accordance with 21 CFR Part 50; and
3. Assuring that all staff and subjects understand and accept the obligations incurred in undertaking this double-blind placebo-controlled study in accordance with 21 CFR Parts 312, 511, 812, 813 and any other applicable regulations.

The research staff is responsible for collecting and recording all clinical data. This includes ensuring that all source documents exist for the data on the Case Report Forms (CRFs), ensuring all fields are completed appropriately, and all corrections are done according to GCPs. Any inconsistencies/deviations will be documented on the CRFs and such findings will be reviewed at the weekly study meetings.

The Project Manager will oversee staff training. Training will include a review of the study protocol, informed consent, telephone screen, CRFs and the procedures that are in place regarding session check-in, data collection, data entry and quality control. All applicable regulations will be reviewed and the roles/responsibilities of each staff member will be explained. All questions will be answered and the training will be documented in a training log, which will be initialed by those involved. The Project Manager will also confirm all appropriate documentation of informed consent and storage of consents in a separate consent binder, and will maintain the study regulatory binder.

The Project Manager, PI ([name]) and Study Physician will work together to confirm eligibility criteria. The Study Physician and PI ([name]) will review charts for each subject on an ongoing basis and will document reviews by initialing and dating each chart, case report forms that contain blood pressure and heart rate measurements, and the medical history and physical form.

The research staff and Project Manager will ensure all medication is properly ordered and received from IDS, stored at the center, labeled, and distributed to subjects.

[name]. is responsible for both staff training and continuing review of completed MINI and C-SSRS interviews.

The data managers will be responsible for creating all CRFs and ensuring that all data will be entered and stored in a manner consistent with the design of the approved CRFs. They will also be responsible for developing the data entry/quality control producers for this study.

Enrollment will be complete when 50 subjects complete all study requirements. On average, 2-3 subjects will be enrolled per month. During the course of the study, safety and data quality monitoring will be performed on an ongoing basis in accordance with the University of Pennsylvania Sponsor-Investigator Standard Operating Procedure PM 504 and any findings will be reviewed on a regular basis with the Investigators at the regular study meeting. The monitoring will include a regular assessment of the number and type of serious adverse events. The first monitoring day will occur no more than two weeks after the first subject is entered.

4.2 Adverse Event Reporting and Monitoring

Adverse Event (AE)

An Adverse Event (AE) is a subcategory of the broader category of "Unanticipated Problems Posing Risk to Subject or Others." An adverse event is defined as:

- Any unfavorable or unintended sign (including an abnormal laboratory finding), symptom, or disease occurring at any stage of the study
- Abnormal results of diagnostic procedures are considered to be adverse events if the abnormality:
 - results in study withdrawal
 - is associated with a serious adverse event
 - is associated with clinical signs or symptoms
 - leads to additional treatment or to further diagnostic tests
 - is considered by the investigator to be of clinical significance
- May include an exacerbation of a pre-existing condition, intercurrent illness or injury, drug interaction, drug overdose, failure of expected action or significant worsening of the disease under study
- An event that may compromise the rights, safety, or welfare of research subjects

Any event that could be characterized by the definitions above is an AE whether or not considered related to the study or product.

Serious Adverse Event (SAE)

Adverse events are classified as serious or non-serious. A **serious adverse event** is any AE that is:

- fatal
- life-threatening
- requires or prolongs hospital stay
- results in persistent or significant disability or incapacity
- a congenital anomaly or birth defect
- an important medical event

Important medical events are those that may not be immediately life threatening, but are clearly of major clinical significance. They may jeopardize the subject, and may require intervention to prevent one of the other serious outcomes noted above. For example, drug overdose or abuse, a seizure that did not result in in-patient hospitalization, or intensive treatment of bronchospasm in an emergency department would typically be considered serious.

All adverse events that do not meet any of the criteria for serious will be regarded as **non-serious adverse events**.

Adverse Event Reporting Period

The study period during which adverse events must be reported is the period from the initiation of any study procedures to the end of the study treatment follow-up. For this study, the study treatment follow-up is defined as 7 days following the last administration of study treatment. A compilation of any Adverse Events will be provided in the annual and final progress reports to NIDA.

Preexisting Condition

A preexisting condition is one that is present at the start of the study. A preexisting condition will be recorded as an adverse event if the frequency, intensity, or the character of the condition worsens during the study period.

General Physical Examination Findings

At screening, any clinically significant abnormality will be recorded as a preexisting condition. At the end of the study, any new clinically significant findings/abnormalities that meet the definition of an adverse event must also be recorded and documented as an adverse event.

Post-study Adverse Event

All unresolved adverse events will be followed by the investigators until the events are resolved, the subject is lost to follow-up, or the adverse event is otherwise explained. At the last scheduled visit, a research team member will instruct each subject to report any subsequent event(s) that the subject, or the subject's personal physician, believes might reasonably be related to participation in this study.

Hospitalization, Prolonged Hospitalization or Surgery

Any adverse event that results in hospitalization or prolonged hospitalization will be documented and reported as a serious adverse event unless specifically instructed otherwise in this protocol. Any condition responsible for surgery should be documented as an adverse event if the condition meets the criteria for an adverse event.

Neither the condition, hospitalization, prolonged hospitalization, nor surgery are reported as an adverse event in the following circumstances:

- Hospitalization or prolonged hospitalization for diagnostic or elective surgical procedures for a preexisting condition. Surgery will **not** be reported as an outcome of an adverse event if the purpose of the surgery was elective or diagnostic and the outcome was uneventful.
- Hospitalization or prolonged hospitalization required to allow efficacy measurement for the study.
- Hospitalization or prolonged hospitalization for therapy of the target disease of the study, unless it is a worsening or increase in frequency of hospital admissions as judged by the clinical investigator.

Medical and scientific judgment should be exercised in deciding whether expedited reporting is appropriate in other situations, such as important medical events that may not be immediately life-threatening or result in death or hospitalization but may jeopardize the patient or may require intervention to prevent one of the other outcomes listed in the definition above. These should also usually be considered serious. Other kinds of events can be labeled "serious adverse events" at the discretion of the investigator.

To ensure no confusion or misunderstanding of the difference between the terms "serious" and "severe," which are not synonymous, the following note of clarification is provided: The term "severe" is often used to describe the intensity (severity) of a specific event (as in mild, moderate, or severe myocardial infarction); the event itself, however, may be of relatively minor medical significance (such as severe headache). This is not the same as "serious," which is based on patient/event outcome or action criteria usually associated with events that pose a threat to a patient's life or functioning. Seriousness (not severity) serves as a guide for defining regulatory reporting obligations.

Severity Grading Scale for Adverse Events

Many disease specific groups have developed toxicity grading scales. For example, most cancer clinical trials use the Common Terminology Criteria for Adverse Events (CTCAE) developed by the NCI. The CTCAE provides a descriptive terminology which is utilized for adverse event reporting. A grading (severity) scale is provided for each adverse event term (<http://ctep.info.nih.gov>). If no guidelines exist, then the following scale can be used:

- Mild: Noticeable to the subject, does not interfere with the subject's daily activities, usually does not require additional therapy, dose reduction, or discontinuation of the study.
- Moderate: Interferes with the subject's daily activities, possibly requires additional therapy, but does not require discontinuation of the study.
- Severe: Severely limits the subject's daily activities and may require discontinuation of the study. This would include all adverse events defined as "serious adverse events".

Attribution/Association with the Drug or Intervention:

An assessment of the relationship between the adverse event and the drug/intervention will be made for each occurrence by the Principal Investigator.

Adverse Event Attribution Categories:

- Unrelated - The AE is clearly NOT related to the intervention
- Unlikely - The AE is doubtfully related to the intervention
- Possible - The AE may be related to the intervention

- Probable - The AE is likely related to the intervention
- Definite - The AE is clearly related to the intervention

4.3 Recording of Adverse Events

At each contact with the subject after the Intake, the study research assistant will seek information on adverse events by specific questioning using a side effect checklist and, as appropriate, by examination. Side effects will be monitored through a two-pronged approach. First, participants will complete a side effects checklist (SEC) at each study visit after the Intake reporting with a frame of reference since their last study visit. The SEC will assess the frequency and severity of common side-effects associated with ramelteon or TN treatment. These items will be rated by participants on a 0 (none) to 3 (severe) scale, and can be summed to provide an overall side effects index.

Second, trained staff will ask participants a non-structured, open-ended question (SEC Open-ended) at each study visit with a one week frame of reference to assess if participants are experiencing any additional symptoms or medical concerns that may be related to their participation in the study.

Research staff are trained to inquire (time of onset, nature of issue reported, possible relation to ramelteon/TN treatment, review of previously reported side effects or concerns, etc.) about any notable side effects or medical concern reported by participants. Any severe (or a pattern of moderate) side effects or notable medical concern will be reported to the Project Manager, Study Physician, and Principal Investigator to determine a course of action (e.g. continue to monitor, reduce medication, stop medication). This consult, including all relevant information, will be documented via email. The Study Physician is knowledgeable of side effects related to ramelteon/TN and is qualified to manage possible side effects.

Based on published reports using the 8mg dose of ramelteon and 21mg dose of TN we expect few side effects and we expect these side effects to be mild and transient in nature. However, in the unlikely event of an adverse event (AE) the study physician will determine the severity of the AE, the relationship of the event to the study drug and decide the course of action for the study subject. The study physician will determine the relationship of toxicity of the study medication as not related, possibly related, probably related, or definitely related using standard criteria.

All adverse events occurring during each study period will be recorded. The clinical course of each event will be followed until resolution, stabilization, or until it has been determined that the study treatment or participation is not the cause. Serious adverse events that are still ongoing at the end of the study period must be followed up to determine the final outcome. Any serious adverse event that occurs after the study period and is considered to be possibly related to the study treatment or study participation will be recorded and reported immediately.

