We estimate it will take a minimum of 7 weeks for a participant to complete the entire study. However, this time period may be longer to accommodate participant schedules or scheduling difficulties between the Intake and phase 1 and the duration of the washout period. Thus, the maximum duration a participant can be in the study is 12 weeks.

Projected date of completion of the proposed study

We estimate that 50 people will have completed the study by March 2018, and that analyses and reporting will be complete by August 2018.

DRUGS OR DEVICES

Ramelteon

The study will be performed using 8mg of ramelteon, which is currently marketed for the treatment of sleep problems.

The proposed study follows the typical dosing regimen for RAM (8mg once a day), which is documented to be safe and well-tolerated [27-29]. Ramelteon will be purchased and packaged into blister packs by the Investigational Drug Service at the University of Pennsylvania. In accordance with FDA recommendations, subjects will be instructed to take study medication within 30 min prior to going to bed and avoid taking study medication with or immediately after a high fat meal.

An IND exemption has been approved for this study for ramelteon and TN as the results will not be reported to the FDA to support a new drug indication.

Supply, Preparation, Storage, Packaging and Dispensing of Study Medication

Ramelteon will be purchased and supplied via the University of Pennsylvania Investigational Drug Service (IDS number pending). Matched placebo will be made in-house using sucrose filler in gel capsules. The IDS will store the medication as per the manufacturer guidelines. Specifically, medication will be stored at room temperature (20 – 25 degrees centigrade) and in airtight containers. Ramelteon and the matching placebo will be packaged in blister packs. IDS will oversee the labeling of all study medication, and will assign each kit, which contains medication for one subject, a unique Pharmacy Randomization Number (PRN).

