12. Complete questionnaires (demographics, nicotine dependence, smoking rate, withdrawal, and smoking urges)
13. Receive instructions on how to record their daily sleep diaries and report their sleep and wake times
14. Be randomized to receive RAM or PLA during the first phase
15. Finalize their study schedule

Participants will be asked to refrain from using any study prohibited drugs (note: participants are allowed to take prescription medications not in the exclusion list) throughout their participation in the study. Female participants will also be asked to use an approved method of contraception through the study.

- Final Eligibility Phone Call (only for individuals with a history of jaundice/liver disease). When liver function tests have been reviewed and authorized by the Study Physician, a study staff member will call the subjects to inform them of their final eligibility.

Final Eligibility is defined as: Liver function test results and GGT liver enzyme levels that are no more than 20% outside the normal, clinical range. Albumin/Globulin ratios 20% outside of normal range will be evaluated for clinical significance by the Study Physician and eligibility will be determined on a case-by-case basis.

Ineligible subjects may be referred to other studies at our center. Eligible subjects will schedule all other study visits and be randomized to receive RAM or PLA during the first phase. During the first study visit, participants will receive instructions on how to use the SensewearPro® and record their daily sleep diaries.

- Baseline Weeks (Weeks 1 and 5). Participants will complete three observation visits during the Baseline weeks on Monday, Wednesday, and Friday. The visits on Monday and Wednesday will last approximately 20 minutes. The start of the first phase can be scheduled within 2 days of the Intake but no more than 30 days can elapse between Intake and start of the first phase. At the observation visits participants will:
 1. Arrive at CIRNA and provide a CO and BrAC sample (Participants must have BrAC readings less than 0.01 in order to be eligible for the study).
 2. Provide a blood pressure sample (See Blood Pressure Procedures under Screening/covariate measures).
 3. Complete questionnaires (smoking rate, concomitant medication review, sleep, withdrawal, smoking urges, mood, and side effects).
 4. Have sleep diaries collected and data stored on armband downloaded by research technician. Research staff will review adherence.

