At the first (Monday) visit of Baseline Week 1 and 5, the participant will receive his or her SensewearPro® armband. At Baseline Week 1, the participant will receive an instructional packet and a research staff member will review how to use the armband and charger correctly.

The third (Friday) visit of each Baseline Week will last approximately 40 minutes. During this visit, subjects will:

1. Provide urine specimens for drug and (if applicable) pregnancy tests (Friday visit only). Participants who test positive for either the urine drug screen and/or pregnancy test will be withdrawn from the study.

2. Meet with a smoking cessation counselor for a 20-min coaching session to prepare them for the practice quit attempt. The counselor will review coping strategies for managing triggers and withdrawal symptoms.
3. Participants will receive their study medication and nicotine patches. Study staff will review instructions for taking the study medication and applying the nicotine patches.

These sessions can be scheduled for any time of day. Ideally, the subsequent sessions would be at the same time of day, but can be scheduled up to 3 hours earlier or later. However, the sessions may go beyond 3 hours as determined by PI discretion.

- Quit Assessment Weeks (Weeks 2 and 6). Participants will attend a 20 minute study visit every weekday of their quit assessment week. They will be asked to bring their study medication to this visit to verify medication adherence/pill counts. During this session, which will last approximately 20 minutes, participants will complete measures of:
 1. Blood pressure (See Blood Pressure Procedures under Screening/covariate measures)
 2. CO breath sample
 - a. To increase abstinence motivation, participants will receive \$10/day (in cash) for each day for self-reported abstinence that is biochemically-confirmed. On Monday, a CO reading of less than 10ppm or less than 50% of CO breath sample taken during the Baseline week will be sufficient as biochemically-confirmed abstinence. At all other visits, a CO reading less than 5 ppm will be considered as biochemically-confirmed abstinence.
 3. BrAC sample
 4. Smoking rate (timeline followback; TLFB)
 5. Medication adherence (pill count)
 6. Side effects and concomitant medication review
 - a. If moderate to severe adverse events are reported, the PI/Study Physician will be consulted and a decision will be made as to whether to proceed with the study.

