Breath Alcohol Concentration. The breath alcohol concentration (BrAC) assessment will be administered at the Intake visit and all subsequent study visits. The breath alcohol monitor assesses expired breath for alcohol content. A reading greater than or equal to 0.01 at any session indicates alcohol consumption within the last 14 hours and will result in the participant being withdrawn from the study.

Activity (Week #)	Intake	Baseline (1 & 5)			Quit Assessment (2 & 6)				
Day	0	Mon	Wed	Fri	Mon	Tue	Wed	Thu	Fri
TREATMENT									
Ramelteon (RAM) or Placebo					X ^a	X ^a	X ^a	X ^a	X ^a
Transdermal Nicotine (TN)					X	X	X	X	X
SCREENING/COVARIATES									
Demographics	X								
Smoking History/FTND	X								
Medical/ ETOH History (self-report)	X								
Psychiatric History (Self-report and MINI)	X								
Suicidal Behavior/ Ideation (C-SSRS)	X								
Urine drug/pregnancy screen	X			X					
Breath alcohol	X	X	X	X	X	X	X	X	X
Blood pressure	X	X	X	X	X	X	X	X	X
Blood draw (liver function tests) ^b	X								
Brief counseling				X					
TREATMENT VARIABLES									
Concomitant Medication Review	X	X	X	X	X	X	X	X	X
RAM Adherence (pill count)					X	X	X	X	X
TN Adherence					X	X	X	X	X
Side Effects (TN and RAM)		X	X	X	X	X	X	X	X
INTERMEDIATE OUTCOMES									
Sleep Diary		X	X	X	X	X	X	X	X
Pittsburgh Sleep Quality Index (PSQI)		X	X	X	X	X	X	X	X
Sleep efficiency (SensewearPro)		X	X	X	X	X	X	X	X
Depression Symptoms (CESD)	X			X					X
Withdrawal, Craving, Affect		X	X	X	X	X	X	X	X
SMOKING OUTCOMES									
Cessation/Smoking Rate (TLFB)	X	X	X	X	X	X	X	X	X
Carbon Monoxide (CO) Test	X	X	X	X	X	X	X	X	X
Note. No visits or assessments during washout (weeks 3-4). FTND=Fagerstrom Test for Nicotine Dependence; CESD= Center for Epidemiological Studies on Depression; TLFB=Timeline Followback a study medication taken the previous night; b only for those with a history of jaundice/liver disease									

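### The open-ended adverse-event question looks back one week while the checklist looks back to the last visit, so about 9 to 10 washout days go unasked for unlisted events

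*Combined protocol and SAP*

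**What the plan says.** Section 4.3 (Recording of Adverse Events) sets out two prongs. Participants complete the side effects checklist "at each study visit after the Intake reporting with a frame of reference since their last study visit". Staff then put a non-structured question about any further symptoms or concerns, "at each study visit with a one week frame of reference". The section does not explain why the look-backs differ. It adds that staff ask about time of onset and go over earlier reports when a side effect or concern is notable.

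The visit schedule is in Study Procedures, Study Visits. For weeks 1 and 5: "Participants will complete three observation visits during the Baseline weeks on Monday, Wednesday, and Friday". For weeks 2 and 6: "Participants will attend a 20 minute study visit every weekday of their quit assessment week". The note under the assessment table in section 3.1 says "No visits or assessments during washout (weeks 3-4"). On a participant's total time in the study, Study Duration says "this time period may be longer to accommodate participant schedules" and names the washout as one of the parts that may lengthen.

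Section 4.2 (Adverse Event Reporting Period) defines one unbroken period, from the first study procedure to the end of follow-up, where "the study treatment follow-up is defined as 7 days following the last administration of study treatment". Under Side Effects, section 3.2 gives participants written instructions to call between visits about severe side effects or adverse events.

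**The concern.** The open-ended question is the only visit-based route by which an event absent from the checklist is recorded. A fixed one-week frame suits weekly visits, but these visits are not weekly. In quit weeks they are daily, so the look-back is longer than the interval and successive windows overlap. Across the washout the interval is more than two weeks, so the look-back is too short and leaves a hole.

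Two things are at stake. One is the completeness of the record for unlisted events in the washout, when effects that outlast period-1 treatment would appear. The other is clean assignment of open-ended reports to treated or untreated days, which matters in a crossover. Adverse-event summaries go into the progress reports to the funder (section 4.2) and the annual data and safety monitoring report. The primary endpoint, the sleep outcomes and the sample size are not affected.

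**Working it through.** **Calendar.** Take day 1 as the Monday of week 1, visits on schedule, and a washout of exactly two weeks.

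- Period 1 visits: days 1, 3, 5 (baseline) and 8, 9, 10, 11, 12 (quit week).
- Period 2 visits: days 29, 31, 33 and 36, 37, 38, 39, 40.
- Total: 2 × (3 + 5) = 16, which reproduces the 16 side-effect assessments stated under Potential Study Risks.

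**Look-back.** One week is read as 7 calendar days including the visit day (visit day minus 6 up to the visit day). The alternative is 8 days, same weekday to same weekday.

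**Washout gap.** The last week-2 visit is day 12 and the next visit is day 29.

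- 7-day reading: the day-29 window starts on 29 − 6 = day 23. Days 13-22 are uncovered: 22 − 13 + 1 = 10 days.
- 8-day reading: the window starts on 29 − 7 = day 22. Days 13-21 are uncovered: 9 days.
- Each day added to the washout adds one day to the gap.
- The checklist at day 29 reaches back 29 − 12 = 17 days and has no gap.

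**First 7 days after period-1 treatment.** Patches are used for 5 days. With a Monday quit date, the last patch is on Friday, day 12.

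- Counting from the Friday patch (day 12): days 13-19, of which 0 of 7 are covered.
- Counting from a Thursday-night capsule (day 11): days 12-18, of which only day 12 is covered, so 1 of 7.

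Both results are the same under the 8-day reading.

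**Quit-week overlap.** The footnote to the assessment table puts each capsule on the night before the visit, so the first is on Sunday night (day 7). The Procedures text, with medication on each weekday, can be read as a first capsule on Monday night (day 8). Those two passages need reconciling; both readings are shown. Counting the day of a bedtime dose as pre-dose, the 7-day window at visit day v holds 14 − v pre-dose days for a Sunday-night start and 15 − v for a Monday-night start.

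| Visit | Mon (8) | Tue (9) | Wed (10) | Thu (11) | Fri (12) |
|---|---|---|---|---|---|
| Sunday-night first dose | 6 | 5 | 4 | 3 | 2 |
| Monday-night first dose | 7 | 6 | 5 | 4 | 3 |

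The 8-day reading adds one to each entry. Period 2 repeats the pattern. A symptom on day 6 or 7 falls inside the window of all five quit-week visits; under a since-last-visit frame it falls in one.

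**After the change.** With the checklist's frame, every day from day 2 to day 40 is covered exactly once. The week-5 Monday visit covers days 13-29 (17 days), including all 7 days after period-1 treatment on either count. Days 41-47 remain uncovered, because no visit follows the Friday of week 6.

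**The case against.** A reader might infer that the protocol breaches its own 7-day follow-up after period 1. The text does not support that. Section 4.2 ties the 7 days to the last administration of study treatment, which read literally comes after week 6, and it defines no follow-up between periods. The washout days matter because they lie inside the continuous reporting period.

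A reader might also infer that adverse-event counts by drug are inflated. That too goes further than the documents. Questions about onset and review of earlier reports guard against repeats and mis-timed events. The Statistical Analysis section plans no comparison of adverse events by drug, and the only summed safety score in section 4.3 is built from checklist items. Both periods share one schedule and order is counterbalanced, so the overlap applies to ramelteon and placebo alike. A risk does remain: the safeguards are written for notable reports only, and no rule says that a repeated report counts once or how it is assigned to a period.

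The gap is narrower than the day count suggests. The week-5 Monday checklist covers the whole washout, and Potential Study Risks says the checklist includes the rare ramelteon effects as well as the common ones. Participants can also phone in. What escapes is an unlisted event that was not phoned in and had ended before the week-5 look-back begins.

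Finally, a short fixed frame limits recall error and gives a second chance to mention something forgotten. That is a fair reason for it within the quit weeks, but it does not help with the washout, where the days are never asked about.

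**Conclusion.** The two look-backs are mismatched, and the open-ended one does not fit the visit schedule. It leaves 9 to 10 washout days with no open-ended enquiry, including at least 6 of the first 7 days after period-1 treatment. All five windows in each quit week reach back before the first dose: by 2 to 6 days with a Sunday-night start and 3 to 7 with a Monday-night start, on the 7-day reading.

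The consequence is incomplete capture of unlisted, unreported events in the washout, plus a possibility, not a demonstrated fact, of repeated or pre-dose reports. These figures assume on-schedule visits, a Monday quit date and the minimum washout; a longer washout widens the gap. This is a modest safety-data point, worth acting on because the remedy is cheap.

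**What to change.** In section 4.3 and on the case report form, ask the open-ended question about the time since the last study visit, as the checklist does. Alternatively, keep the one-week frame in the quit weeks with a stated reason, and use the longer frame at the first visit of each baseline week.

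The cost is one phrase, with no added visit or contact. Recall lengthens to at least 17 days at the week-5 Monday visit (more after an extended washout) and, at the first baseline visit, reaches back to Intake, up to 30 days earlier under Study Visits. The checklist already asks for the same recall at both.

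The change does not reach the 7 days after week 6, where collection rests on participants reporting events themselves (section 4.2, Post-study Adverse Event). The protocol should say so plainly.
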